Weill Cornell Medicine

IRB Protocol Number: 1706018342
Clinicaltrials.gov ID: NCT03467763

Protocol and Statistical Analysis Plan: 07/09/2018

Title: Trial of an intervention to Improve Metformin Persistence and Adherence

Coordinating Center: Weill Cornell Medicine, Department of Medicine

Primary Investigator: [name].

Coinvestigator: [name].

Protocol Version	IRB Approval
Version 1	01/29/2018
Version 2	07/09/2018

Study Overview:

This protocol outlines the design for a randomized controlled trial entitled, "Trial of Restarting and Tolerating Metformin (TreatMet)". Metformin is a safe and effective first-line drug for type 2 diabetes that is also widely recommended for weight loss and diabetes prevention. But, metformin is associated with gastrointestinal and other side effects which prevent its use in 10-20% of patients and appear to limit the usable dose in others. This study is an N-of-1 trial design that will recruit 20 previously metformin-intolerant patients for re-challenge with metformin in a double-blind scenario. In this setting, 'intolerant' means either unable to take metformin at all, or unable to increase the dose past 1,000 mg despite the treating physician's recommendation to do so. Patients will be assigned to take their baseline medication regimen plus 2 weeks of 250 mg per day of metformin extended release, followed by 500 mg metformin XR, 750 mg, and 1,000 mg metformin XR with each treatment period separated by a 2-week course of placebo. Initial treatment, placebo or metformin XR, will be decided randomly. At the end of each two-week treatment period, participants will complete questionnaires assessing overall satisfaction with the medication, gastrointestinal symptoms, and adherence. Six months after the conclusion of the intervention, follow-up will establish if patients are continuing metformin at a higher dose than upon entry to the trial. This trial has two aims. First, to test the hypothesis that medication satisfaction will be the same during periods of placebo treatment and during periods of treatment with the active drug. The second aim is to test the hypothesis that > 30% of metformin-intolerant patients in an N of 1 crossover trial are able to tolerate higher-dose metformin at 6-months.

Relevant Scientific Background:

Despite 60 years of clinical use, and approximately 20 years in which it has been the consensus first-line drug for type 2 diabetes, there are still unresolved translational science questions about metformin. Metformin has only a 50% rate of use among patients with diabetes, and far lower rates of use in patients with obesity and pre-diabetes. In all these groups, poor tolerability related to gastrointestinal side effects is seen as a significant barrier to use. Intolerance can result in non-persistence, poor adherence, or the inability to titrate the dose up to that shown to be efficacious in major studies. One question about metformin intolerance is how often it results from reproducible physical side effects and how often it results from subjective symptoms that are either transient or attributable to placebo effect ("psychogenic intolerance"). Anecdotally, some metformin-exposed patients experience dramatic, objective gastrointestinal side effects that preclude (or dose-limit) its use, while other patients experience vaguer malaise that may be psychogenic. Statin therapy provides a useful analogy: while some statin users experience objectively verifiable myopathy with creatine kinase elevations, others discontinue statin therapy due to much more subjective symptoms. Joy and colleagues found a group of eight patients with a history of statin intolerance could not reliably distinguish between statin and placebo in a crossover re-challenge study, and that half of these patients persisted with statin use long-term after the re-challenge.¹ Particularly in diabetes prevention, the perception by

patients that metformin is worsening their quality of life may be a substantial barrier to long-term use. Research is needed to characterize how often this concern is based on reproducible side effects and how often it is a form of placebo effect. For patients in whom it is due to placebo effect, simple interventions (for example, demonstrating that the side effects are the same with the drug and with a placebo) might eliminate this psychogenic intolerance and make the patient more comfortable with long term use of metformin. For patients who do have reproducible symptoms from metformin use, more research into the risk factors and causes for such side-effects is needed to support development of interventions to make metformin more tolerable.

There are over 14 million unique prescriptions for metformin in the U.S annually, and it is widely regarded as a very safe medication for the treatment of type 2 diabetes mellitus; though side effects do occur. The most frequent adverse events attributable to metformin are primarily gastrointestinal, including nausea, diarrhea, and GI upset. Metformin contains a black-box warning for lactic acidosis, however cases of this occurring nearly are nearly non-existent. One study (Salpeter) found, "There is no evidence to date that metformin therapy is associated with an increased risk of lactic acidosis or with increased levels of lactate compared with other antihyperglycemic treatments if the drugs are prescribed under study conditions, taking into account contraindication".² Furthermore, risk of hypoglycemia is near zero with metformin. The package insert for metformin produced by the FDA states, "hypoglycemia does not occur in patients receiving metformin alone under usual circumstances of use, but could occur when caloric intake is deficient, when strenuous exercise is not compensated by caloric supplementation, or during concomitant use with other glucose-lowering agents (such as sulfonylureas) or ethanol".

From a pragmatic point of view, it has been proposed that for patients who are strongly motivated to use a medication but experience subjective discomfort when using it, an n-of-1 placebo-controlled trial can be a therapeutic intervention. For patients who are having difficulty assessing whether their quality of life is worsened by exposure to a drug like metformin or a statin, undergoing a placebo-controlled double-blinded crossover study and finding that they cannot distinguish between the two could reduce concerns about purely subjective, placebo-driven side effects, and allow patients to use the drug without experiencing those effects. Conversely, if side effects are clearly reproducible with exposure to drug over placebo, patients and their providers could confidently conclude that the drug really is not tolerable for that patient. This idea has been developed to a limited extend in statin use, but has not been applied to diabetes treatments.

Methods:

Patients will be recruited at Weill Cornell Medicine and will be eligible if they have a diagnosis diabetes, pre-diabetes, or obesity, previously attempted to take metformin for one of these indications, and have a history of intolerance to metformin. Intolerance may manifest either as the inability to take metformin at all, or the inability to titrate the dose past 1,000 mg due to side effects. Intolerance will be defined based on the treating

physician's assessment that a history of metformin intolerance (defined as the inability, due to side effects, to use metformin at the otherwise medically appropriate dose) exists, confirmed by the patient's recollection of the same history .

Subject will be recruited that currently have a diagnosis of diabetes, pre-diabetes, or obesity, and possible related comorbidities, but who are ambulatory, independent, and neither seriously nor terminally ill.

Electronic medical records will be reviewed for patients who have been prescribed metformin hydrochloride and for whom the medical record indicates that metformin intolerance occurred and limited the patient's ability to take metformin.

Physicians involved in the clinical trial will identify eligible patients. Once identified, the physician will approach the patient in the clinic at their next appointment and discuss participation in the study. With the permission of other providers at WCMC, such as primary care providers, physicians involved in TreatMet or other study personnel in TreatMet may contact patients by telephone to invite them to participate in this study. Physicians will receive an email, or personal contact inquiring whether they are willing to give the investigators permission to contact specific patients, or to contact patients themselves. Only after obtaining physician approval, patients will be contacted via telephone to invite them to participate in TreatMet. Patients will be contacted during normal office hours. If a patient declines participation, they will not be contacted again. If patients do agree, an in-person meeting for written informed consent will be scheduled. Patients are free to opt-out at any point in this process.

Study Design:

This trial is a self-controlled, double blind crossover study enrolling patients with a clear history of metformin intolerance. Intolerance is defined here as the inability, despite the recommendations of the treating physician, either to take metformin at all, or to increase daily metformin dose beyond 1,000 mg. The study intervention is the addition of 250 mg, 500 mg, 750 mg, and 1,000 mg of metformin daily, to the patient's existing regimen. Up to twenty patients will be enrolled for ten months. For one two-week block they will have 250 mg of metformin extended-release added to their existing regimen, followed by two-week blocks of 500 mg, 750 mg, and 1,000 mg metformin XR, each separated by two-week periods of placebo. The order of treatment assignments will be double-blinded and randomized, except that the 250 mg, 500 mg, 750 mg, and 1,000 mg blocks will always occur in order, smallest to largest.

Primary Objectives:

For aim 1 of this study, the primary objective is to test the hypothesis that patients will have similar treatment satisfaction on metformin and on placebo. The primary outcome of this portion of the study will be the results of the Treatment Satisfaction Questionnaire for Medication. For aim 2 of this study, the primary objective is to test the hypothesis

that > 30% of the patients enrolled in this study are able to tolerate higher-dose metformin at 6 months.

Secondary Objectives:

For aim 1, the secondary objectives are to test the hypotheses that scores on a gastrointestinal symptom questionnaire are not significantly different between placebo and intervention periods; that adherence is not significantly different between periods; and that the answer to the question 'Were you taking placebo or metformin for the past two weeks' is correct no more often than would be predicted by chance.

Statistical Considerations:

With respect to sample size for aim 1, by Lehr's approximation, a sample size of 16 would be needed to identify a 1 standard deviation difference in the mean score on the Medication Treatment Satisfaction Questionnaire. The target sample size is 20 patients to account for possible patient dropout. With respect to sample size for aim 2, by Lehr's approximation, a sample size of 20 provides 95% confidence intervals of approximated +/- 20% around most reported percentages. If the reported rate of success in increasing metformin dose is 30%, the 95% confidence interval around that estimate will range from 10% to 50%. If the reported percentage is 0%, the 95% confidence interval will be approximately 0-15%. We think these are sufficiently precise estimates to help clinicians decide whether n-of-1 clinical trials are a useful intervention for overcoming metformin intolerance.

Inclusion/ Exclusion Criteria:

Patients will be eligible if they are between the ages of 18 and 100. Patients will be recruited in an outpatient setting. Subjects will be enrolled regardless of gender, though a 50:50 ratio of male to female subjects is desirable.

Patients will be ineligible if they have a contraindication to metformin (ie, advanced renal or liver disease, a history of lactic acidosis attributed to metformin, or advanced heart failure). Pregnant women will be excluded from this study due to risk of confounding; pregnant women frequently have nausea and vomiting, changing over time, which if included may invalidate the results of the study.

Assessing Safety and Efficacy:

No data will be collected systematically to monitor safety or efficacy, only tolerability. However, the gastrointestinal symptom questionnaire will serve to quantify gastrointestinal adverse events every 2 weeks. Patients will be educated on potential side effects and risks of metformin and encouraged to both stop the medication and contact the investigators if they experience intolerable side effects or any severe adverse reactions.

Interim and Complete Stopping Rules:

Due to the small sample size, short duration, and limited risks of this study, statistical stopping rules are not specified. Patients are encouraged to speak with their physicians and study coordinators regarding any medication-associated adverse events that may occur as a result of participation in this study.

Adverse Events Collection:

Adverse events that may cause termination or dropout of a subject include hypoglycemia, lactic acidosis, and severe gastrointestinal effects including severe nausea, vomiting, and diarrhea.

Metformin has a well-established safety profile in this clinical setting and no active monitoring for adverse events is planned. Patients who are using diabetes drugs associated with hypoglycemia (sulfonylurea, insulin, or meglitinide) will be advised of the potential for metformin to increase risk of hypoglycemia by potentiating the action of those drugs, and to immediately report any occurrence of hypoglycemia both to the study team and to their regular physician

Adverse events will be graded according to the "Common Terminology Criteria for Adverse Events (CTCAE) v4.0" scale produced by the United States Department of Health and Human Services and the National Institutes of Health. The CTCAE scale rates potential adverse events on a scale from 1 to 5, and is a commonly accepted method of grading adverse events. All adverse events will be recorded on the Office of Research Integrity's "Adverse Event & IND Safety Reporting Cumulative Table". We will report all required adverse events and incidents to NYPH-WCM Patient Services, Risk Management, and/or the Department of Health.

In addition to the IRB, all adverse events recorded during this trial will be reported to [name], and [name].

¹ Joy TR, Monjed A, Zou GY, Hegele RA, McDonald CG, Mahon JL. N-of-1 (Single-Patient) Trials for Statin-Related Myalgia. *Annals of Internal Medicine*. 2014;160(5):301-310

² Salpeter SR, Greyber E, Pasternak GA, Salpeter EE. Risk of fatal and nonfatal lactic acidosis with metformin use in type 2 diabetes mellitus. *Cochrane Database Syst Rev*. 2010;2010(4):Cd002967.

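### Aim 1 hypothesises that metformin and placebo are alike, but gives no margin or rule for 'similar', and for GI score and adherence a non-significant result is itself the hypothesis

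*Combined protocol and SAP*

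**What the plan says.** The Study Overview gives the Aim 1 hypothesis as "medication satisfaction will be the same during periods of placebo treatment and during periods of treatment with the active drug". Primary Objectives weakens this to similarity: "the primary objective is to test the hypothesis that patients will have similar treatment satisfaction on metformin and on placebo". The primary outcome is simply the results of the Treatment Satisfaction Questionnaire for Medication. No summary measure, test, confidence-interval rule or success criterion is attached to it.

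Secondary Objectives lists three further Aim 1 hypotheses:

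- GI symptoms: "scores on a gastrointestinal symptom questionnaire are not significantly different between placebo and intervention periods".
- Adherence: "adherence is not significantly different between periods".
- The patient's guess at treatment "is correct no more often than would be predicted by chance".

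The first two are worded as non-significance; the third is not.

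Statistical Considerations has one figure for Aim 1: "a sample size of 16 would be needed to identify a 1 standard deviation difference in the mean score". The target is 20, to allow for dropout. For Aim 2 the same section discusses the precision of 95% confidence intervals. Aim 1 gets no such discussion.

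On data collection, the Study Overview says "At the end of each two-week treatment period, participants will complete questionnaires".

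**The concern.** A hypothesis of sameness needs a statement of how large a difference still counts as the same. Without one, no satisfaction result is defined that would confirm or refute the primary hypothesis.

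For GI score and adherence the position is worse, because failing to find a difference is the stated hypothesis. Non-significance is not evidence of sameness. It also becomes easier to obtain as the data get weaker, through fewer completers or noisier scores.

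The answer would be used. Relevant Scientific Background presents the finding that a patient cannot tell drug from placebo as the message that could ease worries about side effects. The same section says that some patients have marked, objective GI effects. A worsening that is real but missed would therefore be reported as support for the opposite conclusion.

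**Working it through.** **1. The plan's own figure.** Lehr's rule is n = 16/d² per group. With d = 1, n = 16, as stated. The full formula agrees: 2 × (1.960 + 0.842)² / 1² = 15.7, rounded up to 16, for two-sided 5% and 80% power. The arithmetic is right, but it sizes a two-group test for a difference. It is not a limit for similarity, and the text does not call it one.

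**2. Assumptions for the illustration (none is in the plan).** Score SD 1; within-patient correlation ρ = 0.5; independent period errors; true mean worsening 0.5 SD; two-sided 5% paired t-test on one difference per patient. That difference is the patient's metformin mean minus placebo mean, with SD

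SD_d = √[(1 − ρ)/k_M + (1 − ρ)/k_P + τ²],

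where k_M and k_P are the numbers of metformin and placebo periods used and τ is the between-patient SD of the effect.

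- One period of each, τ = 0: SD_d = √(0.5 + 0.5) = 1, standardised effect 0.5.
- Four of each, τ = 0: SD_d = √(0.125 + 0.125) = 0.5, standardised effect 1.

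**3. Chance of a non-significant result** (noncentral t for uniform effects, simulation for the mixed cases):

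| Case | n = 16 | n = 20 |
|---|---|---|
| One difference per patient, uniform 0.5 SD | 54% | 44% |
| 4 + 4 periods, uniform 0.5 SD, none missing | 4% | 1% |
| 4 + 4 periods, exactly half the patients worsen by 1 SD | 19% | 8% |
| 4 + 4 periods, each patient worsens by 1 SD with probability one half | 25% | 15% |

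With only 12 completers the first two rows become 65% and 12%, so losing patients makes the stated hypothesis easier to confirm. The first row depends on ρ: 74% / 68% at ρ = 0, and 33% / 22% at ρ = 0.7.

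The 4 + 4 layout is slightly favourable. The Study Overview says "Initial treatment, placebo or metformin XR, will be decided randomly", and placebo periods separate the metformin blocks. If no placebo period follows the last block, a patient who starts on metformin has 3 placebo periods, giving SD_d = √(0.125 + 0.167) = 0.54.

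**4. What a similarity claim would need.** Take an illustrative margin of 0.5 SD, true difference 0, and two one-sided 5% tests (90% CI inside both margins).

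- One difference per patient: power 24% at n = 16 and 39% at n = 20. Reaching 80% needs 36 patients.
- With a margin of 1 SD instead: 97% / 99%.

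For the 1,000 mg block alone, with τ = 0.5, generalised least squares on the 7- or 8-period layout (half the patients starting on each treatment) and n − 1 degrees of freedom:

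| Model | 95% CI half-width, n = 16 / 20 | Equivalence power, n = 16 / 20 |
|---|---|---|
| No period term | 0.50 / 0.44 SD | about 30% / 47% |
| Linear period term | 0.61 / 0.54 SD | 10% / 20% |
| Categorical period term | 0.85 / 0.75 SD | about 1% / 1% |

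Power falls because doses always rise in order, so dose is largely aliased with period. Period 8 contains only the 1,000 mg block.

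**The case against.** **Repeated periods may give ample power.** If every period is used, none is missing and the effect is uniform, a 0.5 SD worsening is missed only 4% / 1% of the time. This stands, and it limits the size of the concern. But the plan does not say that all periods will be analysed, or how, and the miss rate rises if only some patients worsen.

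**The 1 SD could be an implied margin.** If it were adopted as a margin on the within-patient difference, 16 to 20 patients would suffice. A reader might conversely infer that the sample size is wrong. Neither follows from the text: the 1 SD is attached to identifying a difference, and whether N is adequate depends on a margin that is not given.

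**The rule for satisfaction.** A reader might infer that the plan will declare satisfaction similar if a test is non-significant. The documents do not say so; that wording is confined to GI score and adherence. Nor does the treatment-guess hypothesis use it.

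**Missing periods.** A reader might infer that the worst metformin periods will be lost. Assessing Safety and Efficacy encourages patients to stop the drug for intolerable effects. It does not say that they stop answering questionnaires. Adverse Events Collection does allow dropout for severe GI effects. Some loss is therefore plausible, but the documents give no basis for putting a size on it.

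**A small exploratory study needs no formal margin.** That is fair if estimation is the intention. The text, however, speaks of testing a hypothesis as the primary objective.

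**Conclusion.** Wrong as written. Two parts rest on the text alone: the primary hypothesis of similarity has no margin or rule, and the GI and adherence hypotheses treat a non-significant result as confirmation.

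The practical size is much less certain. Under the stated assumptions, a real 0.5 SD mean worsening would pass as not significantly different in anything from about 1% to 54% of trials of 16 to 20 patients at ρ = 0.5. The rate depends on how many periods are used and how evenly patients are affected. The fault is the missing rule and the wording. It is not an arithmetic error, and it does not by itself show that the sample size is too small.

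**What to change.** In Primary and Secondary Objectives, with the Study Overview brought into line:

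1. Replace the similarity and non-significance wording with estimation of the within-patient metformin-minus-placebo difference and its 95% CI for satisfaction, GI score and adherence. Use all completed periods. Report the result overall and, descriptively, by dose block.
2. State that sameness or similarity will not be concluded from a non-significant test.
3. Report how many periods are missing because patients stopped for side effects.
4. Only if a similarity claim is wanted, pre-specify a margin justified as the largest tolerable worsening, not carried over from the 1 SD detectable difference. Claim similarity only if the confidence interval excludes that margin.

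Similarity within each dose block should not be a required condition, given the power figures for the 1,000 mg block.

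The cost is wording: no extra patients, visits or data. The drawback is that similarity may not be claimable with 16 to 20 patients, and the sponsor should accept this before choosing item 4.

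### The only named symptom-specific comparison is gastrointestinal, so a patient whose limiting symptom was not gastrointestinal never has that symptom directly compared between metformin and placebo

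*Combined protocol and SAP*

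**What the plan says.** According to the Study Overview, at the end of each two-week period "participants will complete questionnaires assessing overall satisfaction with the medication, gastrointestinal symptoms, and adherence". Under Primary Objectives, Aim 1 rests on satisfaction: "The primary outcome of this portion of the study will be the results of the Treatment Satisfaction Questionnaire for Medication". The Secondary Objectives add three hypotheses:

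- that "scores on a gastrointestinal symptom questionnaire are not significantly different between placebo and intervention periods";
- that adherence does not differ between periods;
- that the patient's guess at the treatment does no better than chance; in part it reads "Were you taking placebo or metformin for the past two weeks' is correct no more often than would be predicted by chance".

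Three other places bear on which symptoms patients may bring into the trial.

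- The Study Overview says that "metformin is associated with gastrointestinal and other side effects".
- Relevant Scientific Background describes some patients with marked, objective gastrointestinal effects, "while other patients experience vaguer malaise that may be psychogenic".
- Methods defines intolerance by side effects without restricting their type. It relies on the treating physician's assessment, "confirmed by the patient's recollection of the same history".

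On adverse events, Assessing Safety and Efficacy has the gastrointestinal questionnaire quantify gastrointestinal events every two weeks. Adverse Events Collection plans no active monitoring. Events are to be recorded and graded, but no comparison between metformin and placebo periods is described.

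**The concern.** The plan wants to know how often intolerance reflects a reproducible effect of the drug and how often it does not. For that purpose, the most informative symptom is the one that made the particular patient stop or limit metformin. If that symptom was gastrointestinal, the questionnaire can compare it on drug and placebo. If it was malaise or something else, no named instrument does.

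The direction of the resulting error matters. The symptom hypothesis is one of no significant difference. A patient whose complaint lies outside the instrument will tend to score alike in both kinds of block, whatever metformin does to the complaint. Such patients pull the average contrast towards zero and so towards the hypothesised result. A flat gastrointestinal score could then be read as showing that patients' complaints were the same on drug and placebo, when for some of them the complaint was not measured.

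**Working it through.** **1. Coverage.** Setting the plan's Aim 1 comparisons against the types of complaint that eligibility admits gives:

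| Comparison between metformin and placebo | Gastrointestinal complaint | Other complaint, such as malaise |
|---|---|---|
| Satisfaction score (primary) | may reflect it | may reflect it, does not identify it |
| Gastrointestinal score | measures it | not designed to measure it |
| Adherence | indirect | indirect |
| Treatment guess | may reflect it | may reflect it, does not identify it |
| Adverse events | quantified every two weeks | only as reported; no comparison planned |

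Nothing in the documents says that the limiting symptom is recorded at entry.

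**2. The plan's own figure.** Statistical Considerations uses Lehr's approximation for a 1 SD difference in satisfaction: n = 16/(1)² = 16. This reproduces; with 16 per group a two-sample comparison has about 81% power at two-sided 5%. The target is raised to 20 for dropout. No sample size or effect size is given for the gastrointestinal score, and no test is named for it.

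**3. Illustration of the dilution.** Everything here except the 20 patients is an assumption.

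- Let f be the share of patients with no gastrointestinal effect of metformin. The documents do not give f; the range shown is 0 to 40%.
- Let d be the mean paired difference in the remaining patients, in units of the SD of within-patient differences. Two values are used: 0.66, chosen because it gives 80% power with 20 patients, and 1, which borrows the size that the plan names for satisfaction.
- The average shift is d(1 − f). The test is a paired t-test, two-sided 5%, with 19 degrees of freedom (critical value 2.093) and noncentrality d(1 − f)√20.

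| f | shift, d = 0.66 | power | shift, d = 1 | power |
|---|---|---|---|---|
| 0% | 0.660 | 80% | 1.0 | 99% |
| 10% | 0.594 | 71% | 0.9 | 97% |
| 20% | 0.528 | 61% | 0.8 | 92% |
| 30% | 0.462 | 50% | 0.7 | 84% |
| 40% | 0.396 | 39% | 0.6 | 72% |

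For f between 10% and 40%, the chance of missing a real difference is therefore 29–61% at d = 0.66 (against 20% with no dilution) and 3–28% at d = 1 (against 1%).

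**4. Sensitivity.** The table keeps the SD of differences at 1. Mixing patients with and without an effect adds variance, so that the SD becomes √(1 + d²f(1 − f)). At d = 1 and f = 40% this is √1.24 = 1.114, the standardised shift is 0.6/1.114 = 0.539, and power is 63% rather than 72%. At d = 0.66 the four diluted powers become 70, 58, 47 and 36%. The loss is somewhat larger, in the same direction.

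**The case against.** The case for the plan has real substance.

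- **Aim 1 does not rest on the gastrointestinal score.** The primary outcome is overall satisfaction, and the treatment guess directly asks whether the patient can tell drug from placebo, which is the reasoning given in the background. Malaise that recurs on metformin could show in both. This stands. A reader might infer that Aim 1 as a whole misses psychogenic intolerance; the documents do not support that, and the gap is confined to the secondary symptom comparison.
- **The gastrointestinal focus is reasoned.** Relevant Scientific Background names gastrointestinal side effects as the main tolerability barrier and the commonest adverse events. The remark on malaise is introduced as anecdotal, and vague gastrointestinal discomfort could also be psychogenic. This stands as a limit on the affected share. It concerns metformin users in general, however, and the documents do not say how complaints divide among the patients to be enrolled.
- **The questionnaire items are not shown.** Either instrument might contain a general side-effect item. That is why the claim is limited to named instruments. The plan still commits to no comparison of a symptom outside the gastrointestinal domain.
- **No patient is classified on the gastrointestinal score.** A reader might infer that the trial would label an individual's intolerance as placebo-driven on that score alone. No such rule exists; the Aim 1 hypotheses concern score differences between periods and the accuracy of the guess.
- **Asking repeatedly about a feared symptom may prime it.** This is possible. The gastrointestinal questionnaire already carries the same risk, and under blinding the priming applies equally in metformin and placebo blocks.

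**Conclusion.** The point holds for the secondary symptom comparison. The gastrointestinal questionnaire is the only named symptom-specific instrument compared between metformin and placebo, while eligibility admits intolerance of any kind. For a patient whose limiting symptom was not gastrointestinal, that comparison does not test the symptom and tends towards no significant difference. Satisfaction and the guess may register such a complaint but cannot say what it was.

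The size cannot be fixed from the documents, because neither the affected share nor the effect on the gastrointestinal score is given. A reader might take the 29–61% miss rate as the expected loss. It depends on a 0.66 SD effect chosen to give 80% power, and with a 1 SD effect the same shares give 3–28%. Both also assume exactly no gastrointestinal effect in the diluting patients. The figures show direction and sensitivity only. The conclusion about coverage does not depend on them, and the primary outcome, Aim 2 and the sample size are unaffected.

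**What to change.** - At consent, record the one symptom that limited metformin, taken from the history that Methods already has confirmed with the patient.
- Add one 0–10 item on that named symptom to each end-of-block questionnaire, with the same wording in metformin and placebo blocks.
- Analyse its metformin–placebo difference as an added Aim 1 secondary outcome beside the gastrointestinal score.
- State in the plan and in the report that the gastrointestinal result applies to gastrointestinal symptoms only.

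The cost is one more item per block and one more secondary analysis, with no extra visit or staff, and the possibility of some priming of the named symptom.
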